10.2 Power Estimates

The primary outcome for the proposed trial is stratified by HIV status and defined as *successful* engagement in care. For HIV-positive participants at baseline, we define successful engagement in HIV care as consistent VS across the 12-month trial (per IOM guidelines²¹⁸). For HIV-negative

or sero-unknown at baseline, we define successful engagement in care as participation in routine HIV testing (2 HIV tests with at least 3 months apart from one another, per CDC guidelines²¹⁹). We define power as correctly identifying the difference in the proportions of YBLMT with serospecific engagement in HIV care within 12 months of each intervention arm (2 arms: HMP Stigma with researcher-created network, HMP Stigma with peer-referred network) to the control arm (Information Control), thus powering for 3 independent hypothesis tests. Our sample size calculations are based on pair-wise HIV-stratified comparisons of the 3 groups in terms of proportion of successful engagement using a two-sided significance level of 0.05 altered by the number of comparisons using a Bonferroni adjustment (significance level is 0.017 for 3 comparisons). To have 80% power to detect a minimum effect size (OR=1.9) of successful engagement in care between the 3-arm trial, we will require at least 450 HIV-negative and 450 HIV-positive participants to detect a 17% difference in successful engagement in. In the event of a 20% loss to follow-up, we will have sufficient power to detect an OR=2.1 (18% difference) at alpha=.017. Participants may continue the study even if they miss an assessment intermittently. We will compare those who completed different follow-up interviews with those who did not on key baseline predictors to check for possible sampling bias. Our analysis will use ITT as appropriate.

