10.3 Statistical Analysis Plan

10.3.1 Specific Aim 1:

Specific Aim 1 is to test whether a smartphone application (app) intervention (HMP Stigma) that promotes user-generated content and engagement to address intersectional stigma is associated with successful engagement in care as compared to an information-only control arm consisting of online informational articles and resources curated for YBLMT. Clinical and demographic characteristics will be described for the entire sample, and by treatment group. These will be compared between treatment groups using ANOVA or Kruskal-Wallis test for continuous variables, and chi-square tests for categorical variables. We will conduct primary analyses of our successful engagement in care outcome using logistic regression analyses to compare each active treatment group to the control in pairwise comparison tests at an adjusted significance level of 0.017 to reduce Type-I errors in our 3-arm trial. This approach allows us to also test for differential efficacy between the two intervention conditions (i.e., Does peer-referral HMP outperform the researcher-created HMP arm?).

Logistic regression analyses will be stratified by serostatus. The regression will be run with group assignment only in the model. Among HIV-positive participants, we will examine how intervention conditions influence YBLMT's likelihood of consistent VS over 12 months. We will also test intervention effects on retention in care per IOM guidelines (i.e., proportion of HIV-positive participants who obtain at least 2 viral load tests (at least 3 months apart) within 12 months). For HIV-negative YBLMT, we will compare the proportion of participants who obtain at least 2 HIV tests (at least 3 months apart) within 12 months across arms. Estimates will be calculated and presented with corresponding 95% exact binomial confidence intervals. In secondary outcome analyses, we will compare arms across other HIV care continuum outcomes, as well as stigmarelated (e.g., reduction in HIV-related stigma) outcomes, using a logistic regression with group assignment on the model assuming no imbalances due to successful randomization.

10.3.2 Specific Aim 2:

Specific Aim 2 is to explore whether user engagement, as measured by paradata, mediates the intervention effects observed in stigma and HIV care outcomes.

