10.4 Missing Data

Several procedures will be used to conduct data analysis when data for either outcomes or covariates are missing. The first step will be to assess the extent and pattern of missing data. If data are missing for only a few cases, then data analysis will be conducted only on study participants with complete data. However, when such a strategy would result in loss of data from a substantial proportion of participants, or if this approach would lead to biased or inaccurate results, then some form of imputation will be performed. The form of imputation used will depend on the nature of the data that are missing. For example, data that are collected repeatedly might be imputed using the "last value carried forward" method; and in some instances, interpolation between neighboring points might also be used.

When the primary endpoint is missing, one data analysis will be conducted using only cases with the endpoint. Subsequent analysis will be done where missing endpoints are imputed. Hot-deck imputation or regression imputation may also be used in this context.

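### The imputed analysis of the primary endpoint has no rule for carrying imputation error, and no missing-not-at-random analysis is planned although the plan allows for 20% loss

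*Combined protocol and SAP*

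**What the plan says.** Section 10.4 has a general paragraph and one specific to the primary endpoint.

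- **General paragraph.** It applies to outcomes and covariates alike. Complete cases are used when little is missing. If too much would be lost, "or if this approach would lead to biased or inaccurate results, then some form of imputation will be performed". No threshold is given. Carry-forward and interpolation appear as examples only: "data that are collected repeatedly might be imputed using the" last value, in some cases.
- **Endpoint paragraph.** "When the primary endpoint is missing, one data analysis will be conducted using only cases with the endpoint". Then: "Subsequent analysis will be done where missing endpoints are imputed". Then: "Hot-deck imputation or regression imputation may also be used in this context". Neither analysis is called primary or sensitivity. No number of imputations, imputation model or variance rule is stated.

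Section 10.3.1 (Specific Aim 1) sets the primary logistic model within serostatus: "The regression will be run with group assignment only in the model". It does not mention missing endpoints.

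Section 10.2 anticipates loss: "In the event of a 20% loss to follow-up, we will have sufficient power to detect an OR=2.1", which it equates with an 18-point difference at 0.017. It also compares completers with non-completers "on key baseline predictors to check for possible sampling bias", and invokes intention to treat where appropriate without saying how missing endpoints are then handled.

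Section 8.1 adds that correlates of attrition will be examined, and that Expectation-Maximization will be used for the longitudinal analyses.

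The note closing section 10.3.3 refers to a Statistical Analysis Plan in which deviations will be documented. The combined document contains no separate text of that kind.

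**The concern.** Two gaps matter for the primary test.

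First, hot-deck and regression imputation are ways of filling in values. Unless the imputation is repeated and the variances combined, or an equivalent correction is made, the analysis treats invented values as data and the standard error is too small. Nothing in the plan rules that out.

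Second, complete cases with a group-only model, and imputation from the same information, both assume that missing participants resemble observed ones in the same arm. The planned checks describe who is missing. They do not show how a result would change if the missing did worse. Because the arms receive different versions of the app, loss related to outcome could differ by arm, and that is the case in which the primary comparison is biased.

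At stake are the error rate if the imputed result is relied on, and the reader's ability to judge how fragile a positive result is.

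**Working it through.** **Inputs.** From section 10.2: two-sided level 0.017 (critical value 2.387), 20% loss, OR 2.1 with an 18-point difference. From section 3.2: 150 per arm in a stratum, so 0.8 × 150 = 120 observed. From section 10.3.1: group-only logistic regression. Assumed, because the documents give no success rate: 50-60% success.

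**1. The plan's own effect.** Counts of 49/120 and 71/120 (assumed, chosen to fit) are 40.8% and 59.2%. The difference is 18.3 points and OR = (71/49)² = 2.10, so the two stated figures agree with each other. Only this pairing is used below, not the power attached to it.

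**2. Error rate of once-only imputation under the null, 20% random loss.** Let pq be the variance of one outcome. Analysing 150 filled values as observed assumes a variance of pq/150 per arm.

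- Arm-mean fill (a group-only regression imputation): the true variance is pq/120. The ratio of assumed to true is 120/150 = 0.80. Error = 2 × [1 − Φ(2.387 × √0.80)] = 0.0328.
- One within-arm hot-deck draw: the true variance is pq × (1/120 + 30/150²) = pq × 0.009667, against an assumed pq × 0.006667. The ratio is 0.690. Error = 2 × [1 − Φ(2.387 × √0.690)] = 0.0475.

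Simulation of 150 per arm at 50% and 60% success agrees: hot-deck about 0.047-0.049, arm-mean fill 0.032-0.033. Complete cases and hot-deck with donors pooled across arms stay at about 0.016-0.018. Multiple imputation with Rubin's rules gives 0.016.

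**3. Outcome-related loss under the null.** Assumed: control loses 20% regardless of outcome; intervention loses 15% of successes and 25% of failures. At 50% true success:

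- success among observed intervention participants = 0.5 × 0.85 / (0.5 × 0.85 + 0.5 × 0.75) = 0.531
- success among missing intervention participants = 0.5 × 0.15 / (0.5 × 0.15 + 0.5 × 0.25) = 0.375, a gap of 15.6 points
- complete-case bias = 0.031; standard error = √(0.25/120 + 0.249/120) = 0.0645; shift = 0.485
- error = [1 − Φ(2.387 − 0.485)] + Φ(−2.387 − 0.485) = about 0.031

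Simulation gives 0.029-0.030 for complete cases at 50% and 60% success. Multiple imputation without auxiliary data gives 0.029-0.030, which is no better. With the matching shift for missing intervention participants it returns to 0.016-0.017. Outcome-related loss that is the same in both arms (10% of successes, 30% of failures) leaves complete cases at 0.015-0.017.

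**4. Tipping point at the plan's effect.** Wald test on the log odds ratio:

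- complete cases: ln 2.10 = 0.742; SE = √(2/49 + 2/71) = 0.263; p = 0.0047
- arm-mean fill analysed as observed: SE = 0.235; p = 0.0016
- missing counted as failure, 49/150 vs 71/150: OR 1.85; SE = 0.239; p = 0.0098

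Multiple imputation with the success probability of missing participants shifted down:

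| Shift (points) | Intervention only: p | Both arms: p |
|---|---|---|
| 0 | 0.0048 | 0.0048 |
| 10 | 0.0119 | 0.0046 |
| 14 | 0.0166 | about 0.0044 |
| 15 | 0.0179 | 0.0044 |
| 20 | 0.0267 | 0.0041 |

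The 0.017 line is crossed between 14 and 15 points when only the intervention arm is shifted and missing controls are like observed controls. It is never crossed when both arms shift equally.

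**The case against.** The strongest defence is that the endpoint paragraph, read naturally, puts complete cases first and imputation second. Section 10.2 points the same way, since it treats loss as a smaller sample with a larger detectable OR. Complete cases keep the nominal level under random loss and under outcome-related loss common to both arms. Imputation is optional wording in a follow-up analysis, and a pooled-donor hot-deck would also hold the level. The attrition checks in section 8.1 are not confined to baseline variables. No section gives loss by arm, so the arm-differential rates and the one-sided shift are assumptions made for this check.

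Most of that stands, and it rules out several stronger readings that a reader might infer:

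- That the plan prescribes single imputation analysed as observed. It permits this and does not state it.
- That the choice of method overturns the result at the plan's effect. The p-values of 0.0016, 0.0047 and 0.0098 are all below 0.017.
- That carry-forward or interpolation is planned for the endpoint. Both are examples for repeated data in general.
- That complete cases are invalid here. They fail only if outcome-related loss differs by arm.

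Two things are left unanswered. The only imputation methods named for the endpoint come without a variance rule. And describing who drops out, or using Expectation-Maximization in the longitudinal models, does not show how far the primary result depends on outcomes nobody observed.

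**Conclusion.** The point holds in a limited form and is worth correcting before outcomes are seen. The primary analysis is implied rather than named. The imputed analysis could, as written, run at roughly two to three times its nominal level: 0.032-0.033 or 0.047-0.049 against 0.017. That rests on 20% random loss, 150 per arm, 50-60% success, and imputation done once within arm.

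The absence of a missing-not-at-random analysis is a gap in its own right. In the assumed arm-differential example, complete-case error is about 0.03, and plain multiple imputation does not repair it. A result at the plan's own effect survives treating all missing as failures, yet would not survive a 14-15 point shortfall confined to missing intervention participants. That does not predict such a shortfall; the documents give no basis for one. It shows that the planned analyses would not reveal the margin.

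**What to change.** In section 10.4:

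1. Label the complete-case analysis as primary, or name another, before outcomes are seen.
2. For the imputed endpoint analysis, replace hot-deck or regression imputation with multiple imputation and Rubin's rules, by arm and serostatus, using baseline and available follow-up viral load or testing data. The auxiliary data matter: without them, multiple imputation corrects the standard error but adds nothing over complete cases.
3. Add a delta-adjusted or tipping-point analysis in which the shift varies separately by arm. Report missing counted as not successful as a further sensitivity analysis. It cannot stand alone, because it applies one rule to both arms.

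The cost is modest programming, somewhat wider intervals than single imputation would give, and the possibility that a positive claim is shown to be less robust. No extra data collection is needed.

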11.0 HUMAN SUBJECTS

This study will be conducted in compliance with the protocol, International Conference on Harmonization Good Clinical Practice guidelines, and 45 CFR Part 46.

11.1 Participants' Confidentiality

All laboratory specimens, questionnaires, evaluation forms, reports, and other records will be identified by a coded number only, to maintain participant confidentiality. All records with personally identifying information will be kept in a locked, limited access area (such as a locked file cabinet). All computer entry and networking programs will be done with coded numbers only. Clinical information will not be released without written permission of the participant (and parent or legal guardian, when applicable), except as necessary for monitoring by the NIMHD.

Every effort will be made to ensure that study participants are protected from risks. The main risk is breach of confidentiality.

Further risks may be specific to each project and these details can be found in the human subjects section accompanying each research project.

Breach of Confidentiality

A potential risk to participants is violation of confidentiality. We will take the utmost caution to protect the confidentiality of all responses. We will minimize this risk by maintaining confidentiality and discretion throughout all research procedures and data management and analysis.

Participants may be concerned about the security of their data, particularly since it is collected and stored electronically. Our research team has significant experience developing security protocols for Internet-based studies, and we will take a variety of steps to ensure participant security, including using a dedicated server behind a firewall, encryption of data, separation of identifiers from responses, and password-protected access to data. Therefore, we believe that this risk will be minimal.

Certificate of Confidentiality

This research specifically targets a vulnerable population, children (YBLMT ages 15-17). We will take every available step to minimize the risk of identifying/linking data being subpoenaed, stolen, or inadvertently released. First, this study will receive a Certificate of Confidentiality from the NIH. Second, all research staff members are required to complete ethical clearance certification regarding protection of human's subjects through their relevant IRBs. Third, this study will have documented procedures to safeguard against the risk of the linking information being stolen by keeping such information in a locked spaces to which only essential study personnel who have completed CITI certification for human subjects research ethics training (http://citiprogram.org) will have access.

A Certificate of Confidentiality for this project will be sought prior to enrolling participants. As noted on the NIH website (http://grants.nih.gov/grants/policy/COC/faqs.htm#187), a Certificate of Confidentiality will help the research team "...avoid compelled 'involuntary disclosure' (e.g., subpoenas) of names and other identifying information about any individual who participates as a research subject (i.e., about whom the investigator maintains identifying information) during any time the Certificate is in effect." We have applied for and received Certificates of Confidentiality for other NIH-funded research projects, and given the sensitive nature of the data collected for this project, do not foresee difficulty securing one for this study.

11.2 Participants' Confidentiality

11.2.1 Risks

The measurements that are involved in this study require finger pricks to collect blood samples. This procedure may cause local discomfort, bleeding, or bruising. This measurement should not be condisered greater than minimal risk in and of itself given its routine use in general health care delivery.

To minimize the risk of participants feeling uncomfortable about answering personal questions, we will use Computer Assisted Self Interview (CASI) methods for the study's surveys. In CASI, participants read and respond to survey questions on a laptop, tablet, smartphone.

To minimize risks to confidentiality, we will secure study data with all appropriate physical, electronic and operational protections. Data will be stored in a physically secure environment. All data files will have encryption and strong password protection. Any identifiable data will either be stored on University of Pennsylvania or UNC-CH's secure servers or will be on fully encrypted laptops. CASI surveys and online eligibility screening will take place on an encrypted commercial survey website, Qualtrics. This site has been used by the investigators for numerous online surveys with MSM with no data security breaches. Access to data will be on a role-based standard; only those study staff who require access to each type of data to complete their study-related roles will be allowed access. All study staff will be trained in security and confidentiality procedures, and will sign a confidentiality agreement before receiving access to any participant data.

We will also develop procedures to minimize indirect disclosure that a participant is participating in an HIV-related research study, or a study that enrolls MSM and transgender women. No study-related messages will ever mention HIV prevention or the nature of the research study. Additionally, all scripts for email, text message, and telephone contact with participants will be reviewed and approved by the University of Pennsylvania's IRB before being used for contact with participants (see "HMP SOP-Communications.docx").

We use SSL encryption for transfers of information online. Qualtrics uses Transport Layer Security (TLS) encryption (also known as Hypertext Transfer Protocol Secure (HTTPS)) for all transmitted data. Survey data are protected with passwords and HTTPS referrer checking. The data is hosted by third party data centers that are Statement on Standards for Attestation Engagements (SSAE)-16 Service Organization Control (SOC) II certified. All data at rest are encrypted, and data on deprecated hard drives are destroyed by U.S. Department of Defense methods and delivered to a third-party data destruction service.

Qualtrics deploys the general requirements set forth by many Federal Acts including the Federal Information Security Management Act (FISMA) of 2002. They meet or exceed the minimum requirements as outlined in Federal Information Processing Standards (FIPS) Publication 200. All client data are considered confidential, and treated as such.

Related to HIPAA, Health Information Technology for Economic and Clinical Health Act (HITECH) are updated assessment rules to ensure that data are properly protected and best security practices are followed. By using secure and certified data centers, Qualtrics ensures the highest protection and testing as per HITECH requirements. We will use Dedoose software to perform all qualitative analyses. Dedoose is a web-based application for organizing and analyzing textual, audio, and video data (qualitative) along with outstanding functionality for their integration with survey, test score, ratings, and demographic data (quantitative). Dedoose employs the highest levels of data encryption available for a web application in all data storage, back up, and

transmission. Dedoose allows for project specific encryption feature. When using this feature, only [name] or her designee will hold the additional encryption key needed to be entered in order to view the project. This gives [name] exclusive control over who can view the project under any circumstances.

In addition to a Certificate of Confidentiality, we will protect participants in the following ways (which correspond to the potential risks described in 8.3):

1) Breach of confidentiality: We will take every precaution to minimize risks to study participants. All research staff members are required to complete ethical clearance certification regarding protection of human subjects through UNC-CH or U. Penn. We also have a strong data and safety monitoring plan in place to protect participants. Adverse events will be reported to the U. Penn IRB, individual research PI institutional IRBs using Adverse Event Reporting Forms created by the research team. Reports will be sent within 24 hours of notification by the PIs. Annual updates on enrollment and retention will also be sent to the IRBs.

All study personnel names on this application have completed training and received certification in Human Subjects Research Protection (CITI Program) and HIPAA regulations. They will continue to renew this training in compliance with institutional policies.

11.2.2 Benefits

The risk to individual participants is small and the potential benefit to both the individual and society is substantial. The main benefit of the proposed study to society is the development of a potentially feasible and acceptable mobile platform that reduces intersectional stigma and improves individuals' adherence to the HIV care continuum (i.e. increased testing for YBLMT without HIV; adherence to treatment for YBLMT living with HIV). Participants may experience improvements in their own experiences with stigma, thereby potentially reducing their risk for HIV infection, transmitting HIV, and the associated risks and costs to society. Therefore, the risk/benefit ratio is favorable. Study participants will be compensated for their time.

Black/African American YMSM account for the highest number of new HIV diagnosis of all YMSM, followed by Hispanic/Latino YMSM.²²¹ If successful, our intervention will improve these outcomes in our subject population. Given this high potential impact and low potential hazards to participants, we find that a clear examination of these research questions outweighs the previously mentioned risks. The effectiveness of a novel, scalable, technology driven intervention to address intersectional stigma is understudied with this population. Given the significant adverse health outcomes associated with HIV infections, and the paucity of intervention programs for this population of young adults, the knowledge to be gained from this research is significant. The risks to participants are reasonable in relation to the importance of the knowledge to be gained.

